3.2 Primary Study Endpoints

The primary endpoint will be achieving $\geq 10\%$ total body weight loss (TBWL).

3.3 Secondary Study Endpoints

The secondary endpoints will be:

1. Evaluating the effect of the weight loss on the adolescents' overall health and mental health using the well-being questionnaires, CES-D and SCAS, prior to IGB insertion, while the IGB is in place, and after the IGB removal.
2. Assessing the effect of weight loss on obesity side effects by monitoring changes in liver enzymes, fasting insulin, HgA1c, and lipid profile.

3.4 Primary Safety Endpoints

- Incidence of all serious adverse events including unanticipated adverse effects (balloon migration, small bowel obstruction, luminal GI perforation, ulcer formation, liver abscess formation, bleeding, biliary obstruction or injury, aspiration, infection, abdominal pain requiring hospitalization, nausea and dehydration requiring intravenous fluids, and death). All adverse events will be captured and graded for severity using Common Terminology Criteria for Adverse Events (CTCAE) scale. [27]
- Early balloon intolerance requiring removal.
- Balloon deflation rates (see Orbera PMA)

4 Subject Selection, Enrollment and Withdrawal

Adolescents age 14-17 who are seen at Mayo Clinic-Rochester in community pediatrics, pediatric GI, pediatric endocrinology, or the pediatric weight management clinic, or at Mayo Clinic Health System (MCHS) with a $BMI > 35 \text{ kg/m}^2$ with one severe comorbidity or $BMI > 40 \text{ kg/m}^2$ with two or more mild comorbidities as per the ESPAGHAN guidelines for

bariatric intervention in children with severe obesity. [14] Recent meta-analysis supported the safety and benefit of IGB use in higher BMI (range 35-55).[24] Subjects that meet these criteria can be referred to the PI, co-investigators, or study coordinator to approach for possible participation in this research study.

4.1 Inclusion Criteria

This study will aim to recruit adolescents age 14-17 years with the BMI criteria and the comorbidities summarized in Table 1.

Table 1: Primary inclusion criteria for bariatric intervention in adolescents:

BMI>35 kg/m² with **one** of the following **severe comorbidities, both for at least 2 years:**

1. Type 2 diabetes mellitus
2. Moderate-to-severe sleep apnea
3. Pseudotumor cerebri
4. NASH based on fatty infiltration of the liver with transaminitis that cannot be explained by other liver disease

Or

BMI>40 kg/m² with **two or more** of the following **mild comorbidities, all for at least 2 years:**

1. Hypertension
2. Dyslipidemia
3. Mild obstructive sleep apnea
4. Chronic venous insufficiency
5. Panniculitis
6. Urinary incontinence
7. NASH
8. Gastroesophageal reflux disease
9. Arthropathies related to weight

Table 1 modified from [14].

In addition, **all** of the following inclusion criteria must be met. The subject must have:

1. attained approximately 95% of adult stature, as demonstrated by Tanner Stage IV or more and growth charts demonstrating the taper/plateau of height as a marker for achieving 95% of the subject's adult stature. Height will be measured by trained staff to the nearest 0.1 cm using a stadiometer attached to a wall and documented in the subject's EMR. In the absence of previous growth charts, skeletal maturity will be documented by a bone age of at least 13 years in girls and 15 years in boys; and
2. failed to attain a healthy weight with at least one experience with medically supervised lifestyle changes, including physical activity and dietary interventions, which will be clearly documented in the subject's medical record, and

3. demonstrated commitment to psychological evaluation perioperatively, in which the pediatric psychologist with expertise in childhood obesity must confirm that the subject has the maturity and stable psychosocial environment necessary for this research study and has validated the CES-D and SCAS surveys completed by the subject, and
4. agreed to avoid pregnancy for 1 year after IGB placement through abstinence or approved contraception as noted in Appendix A (female subjects only), and
5. agreed to adhere to nutritional guidelines after IGB placement, as provided by weight management clinic dietitian, and
6. decisional capacity and desire to provide informed assent in conjunction with parent/guardian consent, and willingness to comply with all study requirements, and
7. hypertension stage I: systolic blood pressure and/or diastolic blood pressure $\geq 95^{\text{th}}$ percentile, OR high normal blood pressure between the 90th and 95th percentile.

Note: Patients with hypothyroidism that is treated and persist to have morbid obesity despite adequate thyroid replacement therapy can be recruited.

4.2 Exclusion Criteria

Subjects will be excluded if:

1. they are pregnant or breastfeeding, or
2. there is any other disease, physical examination finding, or clinical laboratory result that provides a reasonable suspicion of a disease or condition that contraindicates the use of the investigational device or that may affect the interpretation of the results or render the subject at high risk for treatment complications, or
3. there is alcohol, tobacco, or substance use by the subject, or
4. in the opinion of the PI and/or co-investigators, subject or parent/guardian may be non-compliant with study schedules or procedures, or
5. there are any endoscopic contraindications, including large hiatal hernia (≥ 2 cm), esophagitis of any degree, erosive gastritis, or ulceration of the stomach or duodenum, or
6. *H. pylori* is detected via a fecal antigen study prior to initial endoscopic assessment (sensitivity $> 96.8\%$); once treated, a repeat fecal antigen must be performed to document eradication prior to the first endoscopic approach for balloon placement, or
7. they have hypertension stage II $> 99^{\text{th}}$ percentile, unless they had a complete workup to exclude secondary etiologies other than being overweight, or
8. Gastroesophageal reflux disease (GERD) subjects are on more than one medication or have a history of erosive esophagitis due to GERD, or
9. they have dyslipidemia, if part of hereditary metabolic syndrome or genetic disorder, or
10. they have any gastrointestinal disease that can result in stomach ulcerations, such as Crohn's disease, celiac disease, eosinophilic esophagitis, acute or chronic pancreatitis or gastrinoma, or
11. they have any endocrine disorders that affect metabolic status of the subjects, such as untreated hypo/hyperthyroidism, type 1 diabetes, Cushing's disease, or adrenal

insufficiency, as documented in the EMR through an evaluation by the pediatric endocrinologist who will order additional testing if needed, or

12. they have prior gastrointestinal surgery with sequelae, i.e. obstruction, and/or adhesive peritonitis or known abdominal adhesions and/or history of abdominal and/or pelvic surgery which may cause adhesions (except one of the following: caesarean section, diagnostic laparoscopy, laparoscopic appendectomy, laparoscopic cholecystectomy performed 12 or more months prior to balloon implantation), or
13. they have prior open or laparoscopic bariatric surgery, or
14. they have prior surgery of any kind on the esophagus, stomach or any type of hiatal hernia surgery, or
15. they have any inflammatory disease of the gastrointestinal tract including esophagitis, Barrett's esophagus, cancer or specific inflammation such as Crohn's disease, or
16. they have potential upper gastrointestinal bleeding conditions such as esophageal or gastric varices, congenital or acquired intestinal telangiectasis, or other congenital anomalies of the gastrointestinal tract such as atresias or stenoses, or,
17. they have a gastric mass, or
18. they have acid reflux symptoms to any degree that require more than one medication for symptom control, or
19. they have a structural abnormality in the esophagus or pharynx such as a stricture or diverticulum that could impede passage of the balloon alongside the endoscope, or
20. they have achalasia or any other severe esophageal motility disorder that may pose a safety risk during the removal of the device, or
21. they have severe coagulopathy, or
22. they have poorly controlled diabetes, defined as having a HgA1c > 10, or
23. they have serious health conditions unrelated to their weight that would increase the risk of endoscopy, or
24. they have chronic abdominal pain, or
25. they have motility disorders of the GI tract such as gross esophageal motility disorders, gastroparesis, or intractable constipation, or
26. they have hepatic insufficiency or cirrhosis, or
27. they have serious or uncontrolled psychiatric illness or disorder that could compromise their understanding of, or compliance with, follow-up visits and removal of the device, or
28. they are receiving daily prescribed treatment with aspirin, anti-inflammatory agents, anticoagulants or other gastric irritants, or
29. they are taking medications on specified hourly intervals that may be affected by changes to gastric emptying, such as anti-seizure or anti-arrhythmic medications, or
30. they are taking corticosteroids, immunosuppressants, or narcotics, or
31. they are unable or unwilling to take prescribed proton pump inhibitor medication, or
32. they are known to have, or suspected to have, an allergic reaction to materials contained in the system, or
33. they have ever developed a serotonin syndrome and are currently taking any drug known to affect the levels of serotonin in the body (e.g. selective serotonin reuptake inhibitors, serotonin-norepinephrine reuptake inhibitors, monoamine oxidase inhibitors), or

34. they have a medically identifiable cause of obesity (specific diagnosed genetic or hormonal case for obesity such as hypothyroidism or Prader Willi syndrome), or
35. they have known history of endocrine disorders affecting weight, or
36. they use any medications, except for Metformin, known to affect body weight and carbohydrate or lipid metabolism, or
37. they used an intragastric device prior to this study, or
38. they participated in any clinical study which could affect weight loss within the past 6 months, or
39. they have symptomatic congestive heart failure or cardiac arrhythmia, or
40. they have a diagnosis of an autoimmune connective tissue disorder (e.g. lupus, erythematous, scleroderma), or immunocompromised, or
41. they are on insulin for type 2 diabetes and not proficient in self-monitoring capillary blood glucose testing.

4.3 Subject Recruitment, Enrollment and Screening

IRB approved fliers will be distributed to physicians in the following areas, informing them about this study and the primary inclusion criteria: Mayo Clinic-Rochester community pediatrics, pediatric GI, pediatric endocrinology, and the pediatric weight management clinic; and Mayo Clinic Health System (MCHS). The primary inclusion criteria listed will be a $BMI > 35 \text{ kg/m}^2$ and one severe comorbidity or $BMI > 40 \text{ kg/m}^2$ with two or more mild comorbidities. Adolescents age 14-17 who meet these primary inclusion criteria can be referred to the PI, co-investigators, or study coordinator to approach for possible participation in this research study.

Potential subjects will be seen by a pediatric gastroenterologist ([name]) or pediatric endocrinologist ([name]) who will review and approve the potential subject's inclusion and exclusion criteria. For interested subjects who have met all the inclusion and exclusion criteria, a study team member will review the risks, benefits, and alternatives with the subject and his/her parent/guardian. Sufficient time will be given to the subject and his/her parent/guardian to have all questions addressed by the study team and reflect on the decision to participate. If the subject and his/her parent/guardian are freely willing to proceed, a study team member will obtain assent from the subject and consent from the parent/legal guardian. After consent, the subject will be given three questionnaires to complete at home and return at the baseline visit; the PN Q will be returned to and reviewed by the dietitian in the weight management clinic, and the CES-D and SCAS will be returned to and reviewed by the psychologist.

At baseline, subjects will be seen by the pediatric weight management multidisciplinary team consisting of a pediatric gastroenterologist ([name]) or a pediatric endocrinologist ([name]) for a physical examination; a registered dietitian in the weight management clinic; and a psychologist. Blood, urine, and stool samples will also be collected at baseline. The baseline requirements may all be completed in one day, or they may be completed on separate days depending on scheduling times and the subject's availability. Female subjects will also have a urine pregnancy test in the morning before the procedure.

If the subject still meets all the inclusion and exclusion criteria after the baseline evaluations and the pregnancy test are completed, s/he will undergo an endoscopic placement of the IGB balloon by a gastroenterologist and proceed with the remainder of the study as outlined in Section 6.

4.4 Early Withdrawal of Subjects

4.4.1 When and How to Withdraw Subjects

Subject will be withdrawn from the study:

- Subject safety issues, adverse device effects
- Failure of subject to adhere to protocol requirements
- Subject decision to withdraw from the study (withdrawal of consent)

4.4.2 Data Collection and Follow-up for Withdrawn Subjects

If a patient is withdrawn from the study for reasons other than severe adverse events, the IGB will be removed from the patient at a time that works for the patient and within 6 months of insertion. The patient will be followed as per the standard clinical protocol for the IGB to ensure safety. Weight and safety data will be collected until the IGB is removed. After IGB removal subjected will be followed clinically as per our protocol for additional six months to ensure safety.

5 Study Device

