5.4 Subject Compliance Monitoring

The Orbera IGB will be advanced to the stomach under endoscopy guidance and inflated with approximately 600 ml of normal saline. Subject transient nausea and pain symptoms will be managed with few days course of antiemetic and antispasmodics as per our clinical practice. Subject and their parents will then receive a phone call by a GI nurse at 4 days after the procedure (\pm 1 day), then 2 weeks (\pm 1 week), at 1 month (\pm 1 week), and monthly thereafter (\pm 1 week) when not being seen for a physical exam and in the weight management clinic at months 3, 6, 9, and 12 (\pm 1 week), per the clinical protocol visit schedule for the IGB as indicated on Table 2. The PI will evaluate all subjects if the GI nurse feels they need to be evaluated based on results of telephone questionnaire.

At 6 months (\pm 1 week), the subject will return for balloon removal at the pediatric endoscopy unit under monitored pediatric anesthesia care. During this visit, the subject will have blood samples drawn; a physical exam by pediatric gastroenterologist ([name]) or pediatric endocrinologist ([name]), followed by a meeting in the weight management clinic with the dietitian. Following the blood samples, PE, and WMC, the balloon will be removed at the same visit using the standard balloon retrieval kit approved by the FDA.

After balloon removal, all subjects will continue to be followed by the weight management team as indicated on Table 2. Weight, height, waist circumference, and demographic information will be collected at baseline, 3 months (\pm 1 week), time of balloon removal (6 months \pm 1 week), 9 months (\pm 1 week), and at 12 months (\pm 1 week).

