- If pancreas enzymes are $> 3X$ upper limit of normal for institution,
 - In a systemically ill patient with evidence of severe acute pancreatitis (requiring > 3 days hospitalization, OR evidence of end organ damage [acute renal failure, respiratory distress, or meeting SIRS (systemic inflammatory response syndrome) criteria for sepsis], OR cross sectional imaging suggestive of severe acute pancreatitis [evidence of pancreas necrosis or new pseudocyst], the balloon will be removed and close clinical follow-up of these severely ill patients will be required.
 - In a patient who does not meet the criteria of severe pancreatitis, pancreas enzymes will be repeated in 48 hours with clinical follow-up.
- If pancreas enzymes are $< 3X$ upper limit of normal for institution,
 - In a systemically ill patient with evidence of severe acute pancreatitis (requiring > 3 days hospitalization, OR evidence of end organ damage [acute

renal failure, respiratory distress, or meeting SIRS (systemic inflammatory response syndrome) criteria for sepsis], OR cross sectional imaging suggestive of severe acute pancreatitis [evidence of pancreas necrosis or new pseudocyst], the balloon will be removed and close clinical follow-up of these severely ill patients will be required.

- If typical pain persists for > 48-72 hours, pancreas enzymes will be repeated in 48 hours with clinical follow-up.
- If pain resolves within 48-72 hours, clinical follow-up will be required.

In addition to the above mentioned endoscopic findings, the balloon would be removed in case of:

- severe anticipated or unanticipated adverse events
- pregnancy
- subject and family request for balloon removal
- risk of continuation of the trial, in the opinion of the PI, due to psychosocial circumstances, noncompliance with the required follow-ups and removal, or if the subject is moving and there is a risk of not being able to remove the balloon at 6 months.

Otherwise, the balloon will stay in place and the subject will be treated symptomatically, as described in Section 6.2.

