4-Female subjects will have a urine pregnancy test in the morning before the IGB insertion. Once the pregnancy test is confirmed negative, then the IGB can be inserted. At this visit, the subject will also be given a wallet card with emergency information, as well as Mayo Clinic brochures regarding the upper endoscopy and intragastric balloon for weight loss.

5-At the 6 month visit, the subject will have blood samples drawn; a physical exam by the pediatric endocrinologist ([name]) or a pediatric gastroenterologist ([name]); and a meeting in the weight management clinic with the dietitian. Following the blood samples, PE, and WMC, the IGB will be removed at the same visit. The 6 month visit and balloon removal may all be completed in one day, or they may be completed on separate days depending on scheduling times and the subject's availability. This will be up to the discretion of the study team. In order to prepare for the IGB removal, the subject will need to be on a liquid diet for 48 hours prior to its removal, and consume nothing by mouth for at least 12 hours prior to the IGB removal.

6-Other tests include:

- CBC with differential
- Electrolytes panel (Sodium, Potassium, Calcium, Creatinine, Chloride, Bicarbonate, BUN)
- Liver function tests (AST, ALT, Alkaline phosphatase, Total Bilirubin, Total Protein, Albumin)
- Nutritional assessment (Fe/TIBC, B12, Folic Acid, 25-Hydroxy Vitamin D, Ferritin)
- Coagulation panel (ProTime/INR, PTT)
- Total Cholesterol/Lipid panel

- Thyroid function tests, PTH
- Insulin
- Glucose
- CRP
- HgA1c
- Urine sample

7-Questionnaires will be given to the subject after consenting to complete at home with a request that they be returned at the baseline visit. The PN Q will be returned to and reviewed by the dietitian at the weight management clinic. The CES-D and SCAS will be returned to and reviewed by the psychologist during the subject's psychological assessment. Any elevations in the CES-D and SCAS surveys will be further assessed during the subject's visit with the psychologist. If clinically indicated, additional psychological assessment and follow-up that may be needed and will be part of the subject's standard of care.

8-At the PE, the subject's height, weight, waist circumference, HR, BP, and demographics will be collected at baseline, 3, 6, 9 , and 12 months.

7 Statistical Plan

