This is a pilot study of 12 subjects only, so results will be largely descriptive. Standard statistical analysis will be performed. We will use t-tests or alternative measures will be used to test whether weight loss was significant from baseline to each of the follow up points.

8 Safety and Adverse Events

All adverse events occurring during the study, including those not meeting the criteria of an Unanticipated Adverse Device Effect (UADE) will be recorded on the appropriate case report form. Records of these events will be maintained and reports submitted to the FDA and IRB according to the regulatory requirements. All adverse events will be reported. Expected clinical adverse events and anticipated adverse device effects are those listed in Section 1.5.2.

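### For withdrawn subjects, 4.4.2 ends weight collection at balloon removal while 5.4 and Table 2 schedule weights to month 12, so the 9- and 12-month weights are at risk unless the schedule is made to govern

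*Combined protocol and SAP*

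**What the plan says.** Section 4.4.2 sets the data rule for withdrawn subjects. Its first sentence concerns withdrawal "for reasons other than severe adverse events" and has the balloon taken out "at a time that works for the patient and within 6 months of insertion". It then says: "Weight and safety data will be collected until the IGB is removed". After removal these subjects are "followed clinically as per our protocol for additional six months to ensure safety". Weight is not mentioned in that last step.

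Two other places set the weight schedule without any exception for withdrawn subjects:

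- Section 5.4: "After balloon removal, all subjects will continue to be followed by the weight management team as indicated on Table 2". The same section lists weights at baseline, 3 months, removal (6 months), 9 months and 12 months, each follow-up visit within one week.
- Table 2 footnote 8 (section 6.8): "height, weight, waist circumference, HR, BP, and demographics will be collected at baseline, 3, 6, 9 , and 12 months".

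These weights have a planned use. Section 2 includes an aim on whether weight loss lasts after removal. Section 7 plans to "test whether weight loss was significant from baseline to each of the follow up points" and gives no rule for missing weights.

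Section 6.4 lists further grounds for early removal, among them "severe anticipated or unanticipated adverse events". It does not say that a subject whose balloon comes out on those grounds is thereby withdrawn.

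**The concern.** The 9- and 12-month weights are the only ones taken after a removal on schedule, so they carry the durability aim. A study team that follows 4.4.2 as written would not collect them from withdrawn subjects; a team that follows 5.4 and Table 2 would. No passage says which takes precedence.

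Subjects who leave may differ from those who stay. If their later weights are not sought and the comparisons use only the weights at hand, the 9- and 12-month results describe a selected group. Each subject is one twelfth of the sample, so even one or two losses matter. Weights that were never taken cannot be recovered at analysis.

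**Working it through.** The plan has no figure to reproduce here: it gives no withdrawal rate and no standard deviation, and the sample size of 12 has no derivation. The check is therefore one of visit timing, followed by illustrations. The Table 2 grid could not be read reliably in the text available, so the schedule is taken from 5.4 and footnote 8.

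**Inputs**

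- Month of removal after withdrawal, *t*: up to 6 (4.4.2).
- Scheduled weights *v*: months 3, 6, 9 and 12, each ± 1 week (5.4; the months also in footnote 8).
- Follow-up after removal: 6 months (4.4.2).
- Sample size: 12 (section 7).
- Number of weights missing at a visit, *k*: 1 to 3, an assumption.

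**Step 1. Which scheduled weights survive**

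- Reading A: 4.4.2 governs and weights stop at removal. Keep *v* ≤ *t*.
- Reading B: the six months after removal include the Table 2 weights. Keep *v* ≤ *t* + 6.
- Reading C: 5.4 and Table 2 override 4.4.2. Keep all.

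| Removal month | Reading A | Reading B | Reading C |
|---|---|---|---|
| 2 | none | 3, 6 | 3, 6, 9, 12 |
| 3, 4 or 5 | 3 | 3, 6, 9 | 3, 6, 9, 12 |
| 6 | 3, 6 | 3, 6, 9, 12 | 3, 6, 9, 12 |

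Reading A would also allow a weight on the day of removal. It never reaches month 9 or month 12.

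Under reading B, one week is 7/30.4375 = 0.23 month. The 12-month visit is reached only if *t* + 6 ≥ 12 − 0.23, that is *t* ≥ 5.77. The 9-month visit needs *t* ≥ 9 − 0.23 − 6 = 2.77.

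**Step 2. What missing weights would do (illustration)**

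The 95% half-width for a mean, in SD units, is t(0.975, n−1)/√n. With *k* missing, the response rate over all 12 lies between r/12 and (r+k)/12 for *r* observed responders, a width of k/12. The values of *r* are assumed.

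| k | n | Half-width (SD) | Against n = 12 (0.635) | Observed response | Range over 12 |
|---|---|---|---|---|---|
| 1 | 11 | 0.672 | 6% wider | 8/11 = 73% | 67% to 75% |
| 2 | 10 | 0.715 | 13% wider | 7/10 = 70% | 58% to 75% |
| 3 | 9 | 0.769 | 21% wider | 6/9 = 67% | 50% to 75% |

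For the mean, suppose the observed 12-month loss equals the pooled 11.27% quoted in 1.5.3 and two subjects are missing with average loss *x*. The mean over all 12 is (10 × 11.27 + 2x)/12:

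- x = −5% (a gain): 102.7/12 = 8.6%
- x = 0: 112.7/12 = 9.4%
- x = 5%: 122.7/12 = 10.2%
- x = 15%: 142.7/12 = 11.9%

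It falls below 10% when x < (120 − 112.7)/2 = 3.65%.

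**Step 3. A related date**

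Section 8.1 ends adverse-event capture 6 months after removal and equates this with 12 months from insertion. For removal at month 2 the two ends are month 2 + 6 = 8 and month 12. They agree only for removal at month 6.

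**The case against.** The strongest reply is that nothing need be lost. The six months in 4.4.2 are a safety follow-up, 5.4 covers all subjects, and 8.1 states the end of follow-up as 12 months from insertion. On that view, reading C is what was meant. That reading is available and loses no scheduled weight. But 4.4.2 states when collection ends for this very group, and a specific rule would ordinarily limit a general schedule. Reading C cannot be relied on until the text says so.

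A reader might infer that any early removal forfeits the 12-month weight. The documents do not support that. Removal for intolerance under 6.2 or on the grounds in 6.4 is not stated to be withdrawal, and those subjects appear to stay on the Table 2 schedule. Section 4.4.1 does allow withdrawal for adverse device effects, so the groups may overlap, but they are not the same.

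A reader might also infer that withdrawals for severe events have no data rule. That is unclear rather than shown. The limiting phrase sits in the sentence on when the balloon is removed; the sentence on weight carries no such limit and stands under a heading for all withdrawn subjects.

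Three more points stand. Section 7 is silent on missing weights, so an analysis of observed weights only is a likely default, not a stated plan. After withdrawal of consent or non-adherence, some weights will be unobtainable under any wording. The study is a largely descriptive pilot, which lowers the stakes; but a description of durability still depends on who is weighed.

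**Conclusion.** The point holds for subjects withdrawn from the study. Under reading A, all those withdrawn with the balloon in place lack the 9- and 12-month weights. Under reading B, they lack the 12-month weight unless removal is at about month 6, and the 9-month weight too if removal is before about month 2.8. Under reading C, nothing is lost. The text does not settle which applies, and the passages must be reconciled.

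The effect falls on the durability aim and the 9- and 12-month comparisons. It is tempting to conclude that the primary result is compromised, or that reported weight loss will be too high. Neither follows: the primary endpoint in 3.2 has no time point, and the bias could run either way, depending on whether withdrawn subjects do worse or better than the rest. The figures for one to three missing weights, the observed response rates and the use of 11.27% as an observed mean are illustrative assumptions. This should be corrected, but it does not invalidate the design.

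**What to change.** Amend 4.4.2 to agree with 5.4 and Table 2. State that weight is sought at 3, 6, 9 and 12 months, counted from insertion, for every implanted subject. Include withdrawn subjects and those with early removal for any reason, severe events among them, unless consent for data collection is withdrawn.

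In section 7, report the rate of at least 10% TBWL over all implanted subjects. Give the range from counting missing weights as non-response and as response, and the number observed at each visit. For the mean, it would help to add the average loss among missing subjects at which the all-implanted mean drops below 10%.

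Separately, reconcile the two end dates for adverse-event capture in 8.1 and make 4.4.2 consistent with the result.

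The cost is a change of wording and a few extra weights, in subjects whom 4.4.2 already follows for six months after removal. Some weights will still be missing, so the rate may have to be shown as a range and may look less favourable.
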